8.11. SECONDARY EFFICACY ANALYSIS

A series of secondary efficacy and exploratory endpoints will be evaluated, as listed in Section 3.5.2 and 3.5.3. All secondary analyses will be conducted in an exploratory fashion with p-values and confidence intervals presented with no adjustments for multiple comparisons. Interval estimates will be generated at the 95% confidence level. Secondary analyses will be conducted on the mITT population and the per protocol population. Since most secondary endpoints will be collected at multiple time points for each participant, generalized linear mixed models will be utilized, as they are appropriate for longitudinal data analyses and can be adapted for binary dependent variables.

Secondary endpoints analyses are used to confirm or support the findings based on the primary outcome analysis. If most of the secondary endpoints show a change in the opposite direction

from the primary efficacy analysis or no direction, we might have less confidence in the primary endpoint.

8.12. MECHANISTIC ANALYSIS

Since many of the mechanistic endpoints will be collected at multiple time points for each participant, statistical models appropriate for longitudinal data analyses will be used. For example, serum samples for cytokines will be collected at Baseline, day 1, 3, and 7 days post transplantation. The GLMM used to compare treatment groups will be of the form:

$$Kynurenine_{ij} = \alpha + \beta_1 \cdot Treatment_i + \beta_2 \cdot Kyn_0 + \beta_3 Week_j + \gamma_i + \gamma_{ij} \cdot Week_j + \epsilon_{ij}$$

This GLMM example treats cytokine as the dependent variable, including fixed effects for treatment group, baseline cytokine, and week, along with random subject intercepts (γ_i) and random subject slopes (γ_{ij}). Link functions appropriate for each dependent variable (i.e. each mechanistic outcome) will be selected, depending on its distributional form. Similar models will be constructed for other mechanistic endpoints.

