3.5.3. Exploratory endpoints

- Measurements of primary and secondary endpoints at day 75±14.
- Time course of instant blood mediated inflammatory reaction as measured by thrombin-anti-thrombin (TAT), C5a and c-peptide levels before, in the middle and after initiation of islet infusion, and 3h post islet infusion.
- Time course of inflammatory chemokines/cytokines as assessed by serum level of CXCL8, CCL2 (MCP-1), CCL3, CCL4, CXCL10 (IP-10), CXCL9 (MIG), IL-6, IL-10, INF- γ , TNF- α , and IL-1 β [pre-infusion, and 24, 72 and 168hrs, and day 14, and 21 after the end of islet infusion].
- Basal to 240 min time course of glucose, and C-peptide derived from the MMTT (day 75±14 to day 365±14).
- The proportion of patients with an HbA1c \leq 6.5% (day 365±14 days post-transplant only)
- Cumulative number of severe hypoglycemia events.
- The proportion of patients with an HbA1c \leq 6.5% at day 365±14 AND are free of severe hypoglycemic events from day 75±14 to day 365±14 inclusive.
- Daily oral Morphine Equivalents on day prior to visit (day 75±14 to day 365±14).
- Proportion of patients remaining on narcotics (day 75±14 to day 365±14).
- RNA expression profile in peripheral blood mononuclear cells (PBMCs) at 168 h post transplantation. RNA analysis will be done in at least 10 patients to guarantee post-treatment sampling in at least 3-4 patients randomized to AAT and 3-4 to control.
- SF-12 Quality of Life score

3.5.4. Safety endpoints:

- Incidence and severity of Adverse Events and Serious Adverse Events
- Standard laboratory tests including hematology (hematocrit, hemoglobin, red blood cells, platelets, white blood cells, differential white blood cell count), clinical chemistry (sodium, potassium, serum creatinine, blood urea nitrogen, total bilirubin, alanine aminotransferase (ALT), aspartate aminotransferase (AST) and coagulation (International Normalized Ratio (INR), partial thromboplastin time (PTT)), at pre-transplant hospital admission and post-transplant hospital

discharge].

- Vital signs, i.e. blood pressure (BP) and heart rate (HR) at pre-transplant hospital admission and post-transplant hospital discharge. ALT/AST, INR/PTT
- Weight loss from pre-transplant value [time frame: day 75±14 and 365±14 after the transplant]
- Serum level of albumin and pre-albumin (absolute and change from pre-transplant value) [time frame: day 75±14 and 365±14 after the transplant].

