6.3. POST-OPERATIVE ASSESSMENTS

All routine measurements for TP-IAT patients will be measured according to current protocols for this patient population. SF-12 Quality of life and reduction in narcotic dose of morphine or equivalent will be obtained from the Islet Longitudinal Outcome Database (ILOD) which has granted this project authorization to use their information. . The following will be assessed during hospital stay and each time or when patients return for drug injection:

6.3.1. Instant blood mediated inflammatory reaction (IBMIR): 3ml of blood will be collected before AAT injection, before, in the middle, and after initiation of islet infusion and 3h post islet infusion. Serum will be collected and stored in -70 ° C for analysis of thrombin-anti-thrombin complex (TAT), C5a, and c-peptide level.

6.3.2. Chemokines/cytokines: A blood sample will be obtained at 0, 24, 72, and 168 h (before AAT injection), and day 14 (before AAT injection), and 21 (before AAT injection) post transplantation to measure chemokine and cytokine expression in the serum using the Lumix machine. Each time 5 ml of blood will be collected and centrifuged; aliquots of serum will be stored in in -70 ° C for further analysis.

6.3.3. DNA testing: A 10 ml whole blood sample will be collected during screening, and stored in -70 °C for isolation of genomic DNA for further analysis. This future analysis may be conducted by the PI or by other researchers who obtain IRB approval for their research. This research may involve genetic studies. The specimens will be labeled with a code that only study personnel can link back to the patient. Researchers outside of this study will not be given a link between the code number and patient's name or any other identifying information. We expect to store the specimens long-term for future studies on disease condition. Participant will not be contacted for additional consent. The investigators will not tell patient what they find out about the patient, nor will contact the patient if a test becomes available to diagnose a condition that a patient might have or later develop. Results will not be placed in the individual participant's medical record.

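### The mechanistic model in section 8.12 tests one average arm difference and cannot test whether the cytokine time courses differ

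*Combined protocol and SAP*

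**What the plan says.** Section 8.12 introduces its equation with "The GLMM used to compare treatment groups will be of the form". The fixed part is "\beta_1 \cdot Treatment_i + \beta_2 \cdot Kyn_0 + \beta_3 Week_j", and the prose repeats it: "including fixed effects for treatment group, baseline cytokine, and week, along with random subject intercepts". Random subject slopes complete the model. Neither the equation nor the prose has a treatment-by-time term, and time enters through one coefficient on Week. The section ends: "Similar models will be constructed for other mechanistic endpoints".

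The endpoint in section 3.5.3 is worded "Time course of inflammatory chemokines/cytokines as assessed by serum level of" 11 named analytes, sampled before infusion, at 24, 72 and 168 h, and on days 14 and 21. Section 6.3.2 has the same late samples ("and day 14 (before AAT injection), and 21 (before AAT injection) post transplantation to measure chemokine and cytokine expression"), as does the cytokine row of Appendix 1. The illustration in 8.12 is shorter: "serum samples for cytokines will be collected at Baseline, day 1, 3, and 7 days post transplantation". Its equation also labels the outcome kynurenine, which is not among the 11 analytes.

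**The concern.** If one coefficient carries the treatment effect, the two mean curves are parallel by construction. The random slopes have mean zero and carry no information about arm. A difference present at 24 h and gone by day 7 is reported as a smaller difference said to hold throughout, and arms that differ in opposite directions early and late can look the same. A single straight line in weeks also cannot follow a rise and fall within the first week, since days 1, 3 and 7 are weeks 0.14, 0.43 and 1.0.

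Section 2.1.2 attributes the expected benefit of AAT partly to anti-inflammatory action, and section 8.3 says the data are to inform a larger trial. When an effect appears, and how long it lasts, is part of what these samples could contribute. For the primary endpoint, section 8.9 plans contrasts at each visit; section 8.12 has no equivalent.

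**Working it through.** Section 8.12 states no figure to reproduce. The check compares the written model with a joint test of the arm differences at all times.

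**Inputs from the documents.** Arms of 32 and 16 (section 3.1); post-transplant times of 24 h, 72 h, 168 h, day 14 and day 21 (section 3.5.3), so t = 1/7, 3/7, 1, 2 and 3 weeks.

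**Assumptions, not from the documents.** Intercept plus residual variance 1 (this defines 1 SD); within-patient correlation ρ of 0.3 or 0.5 before the slope; random-slope SD s of 0 to 0.5 per week; baseline covariate omitted; no missing samples; two-sided 0.05; large-sample approximation.

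**Formulas.** The covariance V has entries ρ + (1−ρ)·[j=k] + s²·t_j·t_k. Let κ = 1/32 + 1/16 = 0.09375, and let d be the vector of true arm differences.

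- Written model: the Week line is common to both arms and drops out of the arm comparison. The estimate is w·d with w = V⁻¹1/(1ᵀV⁻¹1), and its standard error is √(κ/(1ᵀV⁻¹1)).
- Joint test of all five differences: chi-square on 5 df with noncentrality λ = dᵀV⁻¹d/κ.
- Arm-by-time interaction alone: the same form applied to the four successive differences of d, on 4 df.

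**Early transient effect, d = (0.9, 0.45, 0, 0, 0).** With s = 0 the written model gives the plain mean, 1.35/5 = 0.27 SD.

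- ρ = 0.3: SE = √(0.09375 × (1 + 4×0.3)/5) = 0.203, z = 1.33, power 26%. λ = (1.0125 − (0.3/2.2)×1.8225)/(0.7×0.09375) = 11.6, joint power 75%.
- ρ = 0.5: SE = √(0.09375 × (1 + 4×0.5)/5) = 0.237, z = 1.14, power 21%. λ = (1.0125 − (0.5/3)×1.8225)/(0.5×0.09375) = 15.1, joint power 87%.

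Here 1.0125 is the sum of the squared differences and 1.8225 is the square of their sum. A random slope gives later visits less weight, which helps the written model when the effect is early:

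| ρ | s per week | Written model: estimate (SE) | Power | Joint test | Interaction alone |
|---|---|---|---|---|---|
| 0.3 | 0 | 0.27 (0.203) | 26% | 75% | 71% |
| 0.3 | 0.2 | 0.35 (0.215) | 37% | 73% | 63% |
| 0.3 | 0.5 | 0.50 (0.234) | 57% | 71% | 47% |
| 0.5 | 0 | 0.27 (0.237) | 21% | 87% | 86% |
| 0.5 | 0.2 | 0.38 (0.246) | 33% | 83% | 78% |
| 0.5 | 0.5 | 0.52 (0.259) | 52% | 77% | 60% |

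**Constant effect, 0.6 SD at all five times.** Over the same ρ and s, the written model has 64-84% power, the joint test 39-61% and the interaction alone 5%.

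**Single 24-h contrast at 0.9 SD.** Noncentrality 0.9/√0.09375 = 2.94 on 46 df gives 82% unadjusted, and 60% at 0.05/5.

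**The case against.** The strongest reply is that a common effect is a reasonable choice. Study drug is given on days 0, 7, 14 and 21, so a sustained difference is plausible, and the documents nowhere say that cytokines rise and fall within days. This stands: under a constant effect the written term is the more powerful one, so it should be supplemented and not discarded.

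A second reply is that 8.12 calls its equation an example. That gives some latitude, but the section also says that the comparison will take this form and that similar models will follow for the other mechanistic endpoints. The only flexibility it states is the link function, which adds neither an interaction nor categorical time.

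Third, these are exploratory endpoints in a proof-of-concept trial. That is true, and no primary, secondary or safety conclusion depends on them.

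Stronger readings are tempting but not supported:

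- **Days 14 and 21 will be left out.** Section 8.12 omits them only in an illustrative sentence. Sections 3.5.3 and 6.3.2 and Appendix 1 include them, section 8.11 covers the endpoints as listed in 3.5.3, and the formula excludes no visit.
- **The wrong analyte will be analysed.** The sentence after the equation says that cytokine is the dependent variable, so kynurenine is a naming slip.
- **Power falls from 82% to about 20%.** The lower figure ignores the random slope that 8.12 includes. The higher one is a single unadjusted contrast at the time where the effect was assumed largest.

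**Conclusion.** The point holds for the structure of the model. Followed as written, section 8.12 tests an average baseline-adjusted difference between arms, and does so validly. It cannot test whether the time courses differ, nor estimate the difference at a given time. A reader might infer that the model cannot compare the arms at all, but its treatment term does that.

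The structural conclusion follows from the text alone. The size is conditional: about 21-57% power against 71-87% for the joint test under the assumed early effect, and 64-84% against 39-61% the other way under a constant 0.6 SD effect. With an unknown time pattern, neither summary suffices alone. The change is worth making because it is cheap, but it concerns exploratory analyses only.

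**What to change.** Rewrite the model in 8.12 with baseline, arm, time as a category (24 h, 72 h, 168 h, day 14, day 21), arm-by-time terms and within-subject correlation. For each analyte report:

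- the time-averaged arm effect, with its weighting stated;
- the arm difference at each time, with a 95% interval;
- one joint test of the arm differences at all times. An interaction test alone should not replace it, since it misses a constant shift.

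Label all of these exploratory. Choose the transformation or link by each analyte's distribution, as 8.12 already provides. As clerical alignment, replace kynurenine with the 3.5.3 analytes and list all the 3.5.3 sampling times.

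The change needs no new samples, visits or patients. Its cost is a larger model and more unadjusted comparisons: 11 analytes × 5 times = 55 contrasts in a 48-patient trial. An unstructured covariance over five times has 5×6/2 = 15 parameters, so name a simpler subject-level structure as the fallback if it does not fit.

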9. QUALITY CONTROL AND QUALITY ASSURANCE

The investigator is required to keep accurate records to ensure that the conduct of this study is fully documented, and to ensure that CRFs are completed for all subjects according to the study guidelines outlined in the study protocol and database training materials. As part of the quality assurance and legal responsibilities of an investigation, the study site permit authorized representatives of the sponsors and health authorities to examine (and when required by applicable law, to copy) clinical records for the purpose of quality assurance reviews, audits, and evaluations of the study safety and progress. Unless required by the laws that permit copying for recorders, only the coded identity associated with documents or with other subject data may be copied (and all personally identifying information must be obscured). Authorized representatives as noted above are bound to maintain the strict confidentiality of medical and research information that is linked to identified individuals.

Results of all clinical and laboratory evaluations will be maintained in the subject's medical records and the data will be transferred from these source documents directly to the study data base. All data will be entered/imported, stored, and managed in an encrypted database. Access to data entry screens will be user ID and password protected. Each user will be provided with a unique personal ID and password. The Data will be verified for missing data, inconsistencies, and for any necessary medical clarifications. All relevant data queries arising from these checks will be sent to the Investigator for response and signature. After all data is confirmed, it will be locked for further analysis.

In addition, prior to study initiation, current, signed and dated curriculum vitae, CITI training certificates, and financial disclosure statement of PI and co-investigators will be gathered in the regulatory binder, and information will be updated at least every two years.

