6.1. HOSPITAL STAY

6.1.1. Patient recruitment, blinding and randomization

Subjects will be recruited from the clinical offices of Drs. [name] and [name] during their routine preoperative evaluation for pancreas resection and islet transplantation. During their preoperative evaluation, the purpose of the study and the associated consent form will be explained in detail and the participant will be given time to ask questions. If the subject wishes to participate, the proper consent and HIPAA forms will be signed and dated. The consent form may be signed in person in a clinic or via telehealth using an eConsent/doxy.me. On the doxy.me platform the study participant has the ability to download a copy of the signed consent for their record. They will be informed of this and encouraged to download their copy by the study team member who is obtaining consent. The virtual visit video chat feature of this platform allows for questions from the patient to be answered in real time by the study team. The study team member obtaining consent will also have the ability to review the HIPAA authorization form with the patient and obtain a signature through the doxy.me platform. A copy of the signed consent form will accompany the patient to the operating room for documentation of participation in the study.

Consented patients will be screened based on inclusion and exclusion criteria. If patient meets the criteria, they will be randomized to either AAT or control group by block randomization. The PI ([name]) and the clinical PIs ([name], [name], [name], [name]) of this study will be blinded for the assignment of the study treatment. The Investigational Pharmacy at MUSC will prepare drug infusions using aseptic technique under a sterile hood. In the clinic, a trained RN will infuse the drug and monitor for side effects of AAT. These individuals will not be blinded.

Diabetes care will be managed by the Endocrinology team at MUSC led by [name], co-investigator of our trial. The diabetes care is standardized while in the hospital with insulin drip for all patients post-operatively. The drip is then weaned over the first few days with care individualized by the hospital diabetes management team. The discharge plan is then individualized in accordance with ADA standards.

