6.2. DRUG ADMINISTRATION POST HOSPITAL STAY

In the case when patient is discharged before completion of 4 doses of AAT, they will be asked to return to MUSC at the required times to get the investigational drug administered. Starting and ending time of drug administration and the infusion rate will be recorded for each drug administration. Serum AAT level will be measured before and 30 mins after the first drug administration.

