8.5. BLINDING

The study will be conducted in a double blind manner. Identical study treatment infusion packages will be prepared by our clinical trial coordinator. Study subjects, treating investigators, and efficacy endpoint assessors will be blinded to treatment assignments.

The clinical trial coordinator will produce identical sealed envelopes that contain identification of treatment codes. Prior to initiation of the trial, these envelopes will be stored in a locked file cabinet at the coordinator's office in its limited access central file room.

The DSMB will be partially unblinded for the closed reports (data reported by treatment groups "A" and "B" only). However, if it so wishes, it may be completely unblinded at any time during the trial. If the DSMB wishes to be unblinded on a particular subject only, the NIDDK Liaison to the DSMB should email the request to the unblinded biostatistician.

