APPENDIX 1:

Study Phase	Screening	Treatment									Premature Withdrawal
Time points (days relative to transplant)	Screening	Baseline Before Surgery	Baseline After/ During Surgery	Day 1	Day 3	D7	D14	D21	D75	D365	
Visit#	1	2				3	4	5	6	7	
Visit Windows (days)						±2	±2	±2	±15	±15	
Informed Consent	x										
Medical and Diabetes History	x					x	x	x	x	x	x
Inclusion/Exclusion	x										
Immunoglobulin A (IgA)	x										
AAT infusion		x				x	x	x			
TP-IAT			x								
Inflammatory Cytokine Levels		x	x ³	x	x	x	x	x			
TAT, C3a, c-pep	x	x ¹ , x ²									
Serum AAT level		x ⁴									
Blood mononuclear RNA		x				x					
Blood DNA		x									
Plasma for proteomics, siRNA, etc		x				x					
MMTT -240min c-peptide and glucose									x	x	
Adverse Event Recording		x	x	x	x	x	x	x	x	x	x

- 1 Time 0 and 15 minutes after initiation of islet cell infusion in radiology suite.
- 2 Time 3 hours after initiation of islet cell infusion when participant is back in ICU.
- 3 Cytokine profile obtained 24 hours after initiation of islet cell infusion when participant is back in ICU.
- 4 AAT levels will be measured prior and 30mins after the first AAT infusion.

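### Section 9 files all laboratory results in the medical record, and no rule keeps the serum AAT levels taken before and after the first infusion from staff who must stay blinded

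*Combined protocol and SAP*

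**What the plan says.** **Where results go.** Section 9 (Quality control and quality assurance): "Results of all clinical and laboratory evaluations will be maintained in the subject's medical records". The same section moves the data from these source documents into the study database and sends queries to the investigator for an answer and signature.

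**What is measured.** Section 6.2: "Serum AAT level will be measured before and 30 mins after the first drug administration". The footnote to Appendix 1 agrees: "AAT levels will be measured prior and 30mins after the first AAT infusion".

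**Who must not know the arm.** Section 8.5: "Study subjects, treating investigators, and efficacy endpoint assessors will be blinded to treatment assignments". Section 6.1.1 says that the PI and the clinical PIs "of this study will be blinded for the assignment of the study treatment". Of the investigational pharmacy and the infusing nurse it says: "These individuals will not be blinded". Sections 5.3 and 8.5 also mention an unblinded coordinator and an unblinded biostatistician.

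**The one exception to filing.** For DNA testing, section 6.3.3 says: "Results will not be placed in the individual participant's medical record". Nothing similar is said of the AAT levels. The table of contents lists a section 6.3.3 on plasma AAT, but in the body 6.3.3 is the DNA section, so no text sets out how the AAT samples are handled.

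**The concern.** AAT is what the active arm receives, and the placebo contains none. A level before and a level shortly after the first dose therefore carry direct information on allocation. Followed as written, section 9 places that pair in the record used by the clinicians whom sections 6.1.1 and 8.5 want blinded. It also places the pair in a database whose queries the investigator answers.

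Several later decisions by those clinicians feed endpoints:

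- **Insulin.** Section 6.1.1: "Diabetes care will be managed by the Endocrinology team at MUSC led by" a co-investigator. After the initial drip, both the wean and the discharge plan are set patient by patient. Average daily insulin is a secondary endpoint. Insulin independence depends partly on the decision to stop insulin. The β-score is exposed to the extent that it uses insulin dose; the protocol does not list its components.
- **Opioids.** Morphine equivalents and continued narcotic use are exploratory endpoints (section 3.5.3).
- **Adverse events.** The investigator assesses severity and relationship to treatment (sections 7.1.1 and 7.1.3), and safety is part of the study objective.

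Knowledge of the arm could shift any of these without an effect on the islets. Section 8.11 uses the secondary endpoints to support the primary result, so a shift there would colour the overall reading.

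**Working it through.** The plan states no figure on this point, so there is none to reproduce. Two questions need checking: does any rule shield the result, and does the pair reveal the arm?

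**1. Is there a shield?**

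| Result | Kept out of the record? | Storage stated? |
|---|---|---|
| DNA (6.3.3) | Yes | -70 °C, coded label |
| TAT, C5a, cytokines (6.3.1, 6.3.2) | Not stated | -70 °C; no coding or batching stated |
| Serum AAT (6.2, Appendix 1) | Not stated | Not stated |

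Section 8.5 covers packaging, envelopes and DSMB reports, but not revealing laboratory values. The general rule in section 9 is thus the only one that reaches the AAT result.

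**2. How large is the change?**

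From section 5.2: dose 60 mg/kg; 1000 mg in 20 mL, which is 50 mg/mL; placebo given in the same volume. Volume infused = 60/50 = 1.2 mL/kg.

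Assumed, because the documents do not give them: early distribution volume V of 35 to 80 mL/kg and molecular weight of about 52 kDa.

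Rise on AAT = 60/V; dilution on saline = 1.2/(V + 1.2):

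| V (mL/kg) | Rise (mg/mL) | Rise (µM) | Saline dilution |
|---|---|---|---|
| 35 | 1.71 | 33.0 | 3.3% |
| 40 | 1.50 | 28.8 | 2.9% |
| 50 | 1.20 | 23.1 | 2.3% |
| 80 | 0.75 | 14.4 | 1.5% |

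**3. How often does the pair identify the arm?**

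Assumed: baseline b of 20 to 50 µM; rise r of 14 to 29 µM; measurement CV of 5%, 10% or 15% on each value; normal errors; no change on placebo (the small dilution is ignored). The AAT levels in section 2.2.2 are troughs in deficient patients on weekly dosing, so they do not supply b.

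A patient is called AAT if the change exceeds r/2:

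- SD of change on placebo = CV × b × √2
- SD of change on AAT = CV × √(b² + (b + r)²)
- Correct overall = [2 × Φ((r/2)/SD on AAT) + Φ((r/2)/SD on placebo)]/3, weighted for 2:1 allocation

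Middle example, r = 23, b = 30, CV 10%: the SDs are 4.24 and 6.09; Φ(11.5/6.09) = 0.970; Φ(11.5/4.24) = 0.997; correct = (2 × 0.970 + 0.997)/3 = 0.979.

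| CV | Lowest (r = 14, b = 50) | Highest (r = 29, b = 20) |
|---|---|---|
| 5% | 96.4% | 100% (rounded) |
| 10% | 81.7% | 99.8% |
| 15% | 72.7% | 97.7% |

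Always guessing AAT is right in 32/48 = 66.7%. In patients out of 48, that is 32 by guessing, about 35 in the worst cell (0.727 × 48 = 34.9) and about 47 in the middle example (0.979 × 48 = 47.0).

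**The case against.** A reader might infer that blinded staff can read every patient's allocation from day 0. The documents do not support that.

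- **Timing and access.** Day 0 is when the samples are drawn. No text says where they are assayed, whether they are run at once or stored, when the result is reported, or who can open it. The list of required laboratory tests in section 6.1.1 names IgA and the MMTT but not AAT. That list is not exhaustive, but the omission fits a research assay run later. This stands.
- **Certainty.** Identification is likely under most of the assumed values, not assured, and all of those values come from outside the documents. This stands.
- **The wording of section 9.** It can be read as a generic source-document statement, and the DNA exception shows that it is not literally universal. This is fair, but the exception is written down for DNA and not for AAT, so the general rule still applies to AAT.
- **The diabetes team.** Its members are not named as blinded. The co-investigator who leads it is plausibly covered as a treating investigator; the wider team is not clearly covered.
- **Consequence.** The primary endpoint is a laboratory C-peptide AUC divided by IEQ/kg. Insulin independence also needs HbA1c, glucose and C-peptide criteria. Section 8.3 treats all hypothesis testing as exploratory, and section 8.11 does the same for the secondary analyses. This limits the damage but does not remove it for insulin dose, opioid use and adverse-event attribution.

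**Conclusion.** The point holds in a limited form. A stated filing rule, a scheduled assay that reveals treatment and a blinding requirement conflict, and nothing in the plan resolves the conflict. If section 9 is followed as written, the AAT pair would identify the arm in most patients once reported: about 96% to 100% at 5% measurement error, 82% to 99.8% at 10%, and 73% in the least favourable case at 15%, against 67% by guessing. These figures rest on assumed distribution volume, molecular weight, baseline level and error.

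The documents do not show that the blind is broken on day 0, for every patient, or at all if the samples are in practice held back. The primary C-peptide AUC is largely insulated. At risk are average daily insulin, in part insulin independence and the β-score, opioid use, and the grading and attribution of adverse events. This should be corrected, but it does not undermine the primary analysis.

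**What to change.** Add a sentence to each of two sections.

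- **Section 6.2:** both serum AAT samples are labelled with a study code and stored for later assay. Results go only to unblinded staff (the unblinded biostatistician and, on request, the DSMB) until database lock.
- **Section 9:** serum AAT results are exempt from filing in the medical record and are not held in the investigator-facing database, so they generate no queries to blinded staff.

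The cost is a small change in labelling, storage and routing. It has to be written for AAT, because the plan does not state coding or batching even for TAT, C5a and cytokines. No extra samples are needed. No dosing or safety rule in the protocol uses the AAT level (section 5.4.1 foresees no dose modification, and the stopping rules in 5.5 do not mention it), so withholding the result alters no protocol decision. If the samples are already handled this way, the sponsor need only write it down.
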